4.2.2 Demographics and Baseline Characteristics

Demographics, baseline characteristics, medical history and PD treatment history will be summarized for subjects enrolled in the DBE period and subjects not enrolled in the DBE period, respectively. Please refer to the SAP of placebo-controlled period for more details.

4.2.3 Concomitant Medications and Non-Drug Therapies

All medications will be coded using the World Health Organization Drug (WHODrug March 2020 B3 or higher) dictionary. All non-drug therapies (defined as diagnostic procedures or medical treatment procedures) will be coded using the MedDRA dictionary version 23.0 or higher.

The number (%) of subjects taking concomitant general medication (excluding PD medications) and non-drug therapies in the DBE period will be summarized by DBE treatment group for subjects enrolled in the DBE period. In addition, number of subjects in the ITT population that have taken any concomitant medications in the active treatment (placebo-controlled and DBE) period will be summarized. Concomitant non-PD medications and non-drug therapies will be listed in the placebo-controlled and DBE treatment period. Start and stop day in the listing will be computed based on the placebo-controlled baseline.

For subjects enrolled in the DBE period, the number (%) of subjects taking any concomitant PD symptomatic medications, number of subjects taking Dopamine, MAO-B inhibitor, Dopamine Agonist at the baseline of the placebo-controlled period and at the baseline of DBE period will be summarized respectively by DBE treatment group. The placebo-controlled and DBE period data will be summarized in the same fashion. Concomitant PD symptomatic medication will be listed for all subjects in the placebo-controlled and DBE periods. Start and stop day in the listing will be computed based on the placebo-controlled baseline. Please refer to the placebo-controlled SAP for definitions of concomitant therapies and PD symptomatic medication use at baseline.

4.2.4 Protocol Deviations

Protocol deviations identified during site monitoring will be captured in a Protocol Deviation log and categorized as major or minor deviations. The major protocol deviations occurred in

CONFIDENTIAL

The information contained herein may not be used, disclosed, or published without the written consent of Biogen MA Inc.

	Statistical Analysis Plan Dose Blinded Extension Period	V2.0
---	--	-------------

the DBE period will be summarized for subjects enrolled in DBE. The major protocol deviations for all ITT subjects in the combined placebo-controlled and DBE periods will also be summarized. Major and minor protocol deviations for all ITT subjects will be listed, respectively, across the placebo-controlled period and the DBE period. All summaries for protocol deviations will be presented by DBE treatment group. A separate Covid-19 related protocol deviation category will be shown in the protocol deviation listings.

4.2.5 Study Drug Exposure and Study Drug Compliance

A summary table of study drug exposure and compliance in the DBE period will be provided. Number of infusions of BIIB054 received will be summarized as a continuous variable as well as a categorical variable (categories as 1-5, 6-10 and 11-15, 16-20, 20-25, ≥ 26) as well as a continuous variable. Number of weeks on study treatment, calculated as (date of last dose – date of first dose +1)/7, will be summarized as a categorical variable (categories as < 0.5 years, ≥ 0.5 years, ≥ 1 year, ≥ 2 years, ≥ 3 years) as well as a continuous variable. Percentage of study treatment taken up to the last dose, calculated as (the actual number of infusions / the number of infusions a subject is expected to take until the date of last infusion)*100, will be summarized as a continuous variable. This table will be presented by DBE treatment group. A similar table will also be provided on the active treatment (placebo-controlled and DBE) period in order to summarize the exposure data while subjects are on BIIB054.

A listing of study drug administration records, including infusion start date and time, infusion stop date and time, total volume prepared, total volume administered, location of infusion, initial infusion rate, dose interruption or rate change or not, time of interruption or rate change, infusion rate after interruption or rate change, reason for interruption or rate change will be provided for the placebo-controlled and DBE period. A listing of subjects who received the wrong treatment compared to what they were randomized to will be provided for the placebo-controlled and DBE period.

4.3 Efficacy analyses

4.3.1 General Consideration

The analysis population for the efficacy analyses are defined in Section 4.2.1. The analysis period includes data from both placebo-controlled and DBE period combined. That is, data from both the placebo-controlled and DBE periods will be included in the analysis.

The following three comparisons will be evaluated for the long-term efficacy analyses of BIIB054:

- The early start 250 mg compared with the pooled delayed start group;
- The early start 1250 mg compared with the pooled delayed start group;
- The early start 3500 mg compared with the pooled delayed start group

The following comparisons may also be evaluated:

- The early start 250 mg compared with the delayed start 250 mg;

CONFIDENTIAL

The information contained herein may not be used, disclosed, or published without the written consent of Biogen MA Inc.

	Statistical Analysis Plan Dose Blinded Extension Period	V2.0
---	--	-------------

- The early start 1250 mg compared with the delayed start 1250 mg.
- The early start 3500 mg compared with the delayed start 3500 mg.

The pooled delayed start group contains all the subjects who were randomized to placebo treatment in the placebo-controlled period including those who did and who did not enter into the DBE period. There will be no multiple comparison adjustments. Data after subjects start PD symptomatic treatment will be included in the analyses, since the majority of subjects are expected to take PD medication after Week 52.

Subjects who were randomized to placebo group but accidentally received one or more doses of the active treatment during the placebo-controlled period will be classified as delayed start for all the efficacy, pharmacodynamic, and ██████ analyses.

Visit Windows for by visit analyses

For the by visit summaries and MMRM models, the analysis visit should be defined using visit windows (see Tables 6-16 in the Appendix). If there is more than 1 value in the same analysis visit window (>1 value for the same analysis visit) for a certain parameter for a subject, then the closest record to the target visit day will be used for the by visit analysis. If they are with the same distance from the target visit day, then the record with the later time will be used for the by visit analysis.

Handling of missing items for scales

Please refer to the placebo-controlled SAP for the imputation method. The same method will be applied to efficacy endpoints collected in the DBE period.

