2.1.2 Years 2-4 (Active-Treatment Dose-Blinded Portion of the Study)

Prior to Infusion 14 (the first dose of Year 2) at Week 52, subjects who received placebo in Year 1 will be randomized into 1 of the active-dosing arms for Year 2; these subjects will receive BIIB054 in Year 2. Subjects who received BIIB054 (250mg, 1250 mg or 3500 mg) in Year 1 of the study will continue with the same dose regimen in Year 2. Subjects receiving the 250-mg dose in Year 1 continued on their original dose assignment.

CONFIDENTIAL

The information contained herein may not be used, disclosed, or published without the written consent of Biogen MA Inc.

	Statistical Analysis Plan Dose Blinded Extension Period	V2.0
---	--	-------------

Subjects will receive 12 additional doses of BIIB054 (250, 1250, or 3500 mg) in Year 2 and up to 16 additional doses in Years 3 and 4. Up until the last subject in the study has had his or her last dose in Year 2 of the study (Week 96 Visit), eligible subjects will be able to continue treatment once every 4 weeks.

[figure not shown]
Subjects who complete dosing through Week 96 and the Final Visit 12 weeks after the last visit will be considered Year 2 completers in the eCRF.

See Figure 2 for a depiction of the duration of dosing in Years 3 and 4 for subjects continuing dosing past Week 96.

Figure 4 in the protocol presents a flowchart for dosing and procedures from Week 96 through end of study, including how to determine which subjects are eligible to continue dosing past Week 96.

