4 STATISTICAL ANALYSIS METHODS

4.1 General Considerations

This statistical analysis plan (SAP) covers the analyses of the dose-blinded extension (i.e., long term extension) period (Years 2-4) and the analyses across both the placebo-controlled period and the DBE period (analyses integrating the data for Years 1-4).

Summary tables will be presented using descriptive summary statistics. For continuous variables, summary statistics will generally include number of subjects with data, mean, standard deviation, median, 25% percentile, 75% percentile, minimum and maximum. For categorical variables, this will generally include number of subjects randomized or dosed, number with data, and the percent of those with data in each category. Pharmacokinetics (PK) summaries will also include Geometric mean and geometric CV.

Statistical testing will be performed to assess efficacy endpoints by conducting pairwise comparison between each BIIB054 group and the delayed-start group (i.e. subjects who were randomized to placebo in Year-1),. Dose-response relationship may also be tested. Unless stated otherwise, all the statistical tests will be 2-sided with a statistical significance level of 0.05 .

The statistical software, SAS[®] will be used for all summaries and analyses.

Analysis displays

Unless otherwise specified, the analysis of the DBE period and the analyses across both the placebo-controlled period and the DBE period will be displayed by DBE treatment groups as shown below, separate for early and delayed start treatment group) including tables, listings and figures, unless otherwise specified.

Unless otherwise specified, analyses for efficacy data (e.g., pharmacodynamics of imaging, [REDACTED], clinical efficacy, [REDACTED]) will be displayed by the following treatment groups according to randomization assignment at the start of the placebo-controlled period:

- BIIB054 early start: subjects who are assigned to (1) receive BIIB054 in the placebo-controlled period and (2) continue receiving BIIB054 in the DBE period
- BIIB054 late start: subjects who are assigned to (1) receive placebo in the placebo-controlled period and (2) switch to BIIB054 in the DBE period

Unless otherwise specified, analyses for safety, PK, and ADA data will be displayed by the following treatment groups according to dose received:

- BIIB054 early start: subjects who receive BIIB054 in the placebo-controlled period (regardless of randomization assignment)

CONFIDENTIAL

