4.3.2 Primary efficacy endpoint analysis

The estimand of the primary analysis for MDS-UPDRS Part I+II+III total score at Week 72 is the mean difference of the change from baseline at Week 72 between treatment groups in the ITT population regardless of whether start of PD medication had occurred or not. Specifically, the estimand takes the following into consideration:

- A. Population: ITT population as defined in Section 4.1.1;
- B. Variable: change from baseline to Week 72 in the MDS-UPDRS Part I+II+III total score;
- C. Intercurrent events: regardless of whether start of PD medication had occurred or not;
- D. Population-level summary: difference in variable means between each early start group and delayed start group

Change from baseline in the MDS-UPDRS Part I+II+III total score at Week 72 will be analyzed using an MMRM model for all the visits in the placebo-controlled and DBE period.

Data after subjects start PD medication will be included in the primary analyses.

For details on the model to be used please refer back to the Year 1 SAP, for the analyses of MDS-UPDRS including data after PD medication. Adjusted means for each treatment group,

CONFIDENTIAL

The information contained herein may not be used, disclosed, or published without the written consent of Biogen MA Inc.

	Statistical Analysis Plan Dose Blinded Extension Period	V2.0
---	--	-------------

pairwise adjusted differences for the comparisons, 95% confidence intervals for the differences will be presented at each visit, and p-values will be presented for the key visits of week 24, 52, and 72. Dose-response testing will be done using the adjusted mean with the pre-specified MCP-MOD procedure with pre-specified candidate models (refer to Year 1 SAP Sample Size Consideration section). If the distribution of the outcome is highly skewed, p-value will be generated from the MMRM model based on the rank data. Missing data are assumed to be missing at random behind the MMRM model.

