4.6 Pharmacodynamic -Imaging analysis

4.6.1 General Consideration

There are three types of imaging outcomes in the study: DaT/SPECT imaging, Neuromelanin MRI imaging and Structural MRI imaging. Please refer to the placebo-controlled SAP for details.

The analysis population for pharmacodynamic analysis is defined in Section 3.1.1. The analysis period is placebo-controlled and DBE period. That is, data from both the placebo-controlled and DBE periods will be included in the analysis. All pharmacodynamic analyses will be presented by DBE treatment group.

The following three comparisons will be evaluated for the long-term pharmacodynamic analyses of BIIB054:

- The early start 250 mg compared with the delayed start 250 mg;
- The early start 1250 mg compared with the delayed start 1250 mg.
- The early start 3500 mg compared with the delayed start 3500 mg.

The following comparisons may also be evaluated:

- The early start 250 mg compared with the pooled delayed start group;

CONFIDENTIAL

The information contained herein may not be used, disclosed, or published without the written consent of Biogen MA Inc.

	Statistical Analysis Plan Dose Blinded Extension Period	V2.0
---	--	-------------

- The early start 1250 mg compared with the pooled delayed start group;
- The early start 3500 mg compared with the pooled delayed start group

The pooled delayed start group contains all the subjects who were randomized to placebo treatment in the placebo-controlled period including those who did and who did not enter to the DBE period. There will be no multiple comparison adjustments. Data after subjects start PD symptomatic treatment will be included in the analyses.

Visit Windows for by visit analyses

For the by visit summaries and MMRM models, the analysis visit should be defined using visit windows (see Table 3 in the Appendix). If there is more than 1 value in the same analysis visit window (>1 value for the same analysis visit) for a certain parameter for a subject, then the closest record to the target visit day will be used for the by visit analysis. If they are with the same distance from the target visit day, then the record with the later time will be used for the by visit analysis.

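### The same-dose early versus delayed contrasts that the extension plan puts first for imaging are not fully randomised, because a delayed-start dose exists only from Week 52

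*SAP*

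**What the plan says.** All sections below are in the DBE SAP unless noted.

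- **When delayed-start doses arise (2.1.2).** Before Infusion 14 at Week 52, "subjects who received placebo in Year 1 will be randomized into 1 of the active-dosing arms for Year 2".
- **Imaging (4.6.1).** "The following three comparisons will be evaluated for the long-term pharmacodynamic analyses of BIIB054": the list that follows holds the three same-dose contrasts. The pooled contrasts come second, as ones that may be done. Section 4.6.2 gives differences at each visit and p-values at Weeks 24, 52, 96 and 148.
- **Imaging again (4.4).** The main comparison is early against delayed start, and only the pooled delayed-start group is defined.
- **MDS-UPDRS (4.3.1, 4.3.2).** The order is reversed. The pooled contrasts are planned, and the same-dose ones, such as "The early start 250 mg compared with the delayed start 250 mg", stand under "The following comparisons may also be evaluated". Section 4.3.2 names the pooled group as the primary comparator.
- **Who is in each group.** The pooled group holds all subjects randomised to placebo, "including those who did and who did not enter into the DBE period". No such statement covers the dose-specific delayed groups. Efficacy groups are formed "according to randomization assignment at the start of the placebo-controlled period" (4.1), with early start defined as "subjects who are assigned to (1) receive BIIB054 in the placebo-controlled period and (2) continue receiving BIIB054 in the DBE period".
- **Populations.** For Week 72, "Population: ITT population as defined in Section 4.1.1", which means randomised and dosed. Imaging uses the pharmacodynamic population, which also needs one post-baseline measurement.

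**The concern.** A placebo subject who left in Year 1 never received a Year 2 assignment and so belongs to no delayed-start dose group. A subject on BIIB054 who left in Year 1 stays in the early-start group and contributes early visits to the MMRM. The two sides of a same-dose contrast are thus filtered differently after randomisation.

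If faster progressors leave more often, the delayed-start dose groups look better than the arm they came from, and early start looks worse with no drug effect. If slower progressors leave, the sign reverses. The missing-at-random assumption does not repair this: it lets the model recover the mean of a group that includes its dropouts, but these dropouts are not members of the delayed-start dose groups.

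There is a second problem up to Week 52. Every delayed-start subject had been assigned only placebo until then, so a same-dose contrast at Week 24 or 52 is a drug-versus-placebo contrast that uses a fraction of the placebo arm, defined by a later event.

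**Working it through.** **1. The plan's own counts.** Table 3.2 has 101 placebo subjects (8 + 93). At 10% dropout, 8 × 0.9 = 7.2 → 7 and 93 × 0.9 = 83.7 → 84, total 91, as in Table 3.3. At 15%, 6.8 → 7 and 79.05 → 79, total 86, as in Table 3.4. So about 10 of 101 placebo subjects cannot enter any delayed-start dose group.

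**2. Bias at Week 72 with no drug effect (MDS-UPDRS).** From the SAP: SD 13.7 and 10% Year 1 dropout. Assumed: dropout follows a logistic curve in the Week 24 change, with odds 1.5 to 3 times higher per SD of worsening, and a correlation r of 0.5 to 0.6 between Weeks 24 and 72.

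Bias = SD × r × (downward shift of the stayers' mean at Week 24, in SD units).

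- Odds ratio 1.5, shift 0.0399: 13.7 × 0.5 × 0.0399 = 0.27.
- Odds ratio 3, shift 0.0978: 13.7 × 0.6 × 0.0978 = 0.80.

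That is 5% to 15% of 5.28 (55% of 9.6), or 5% to 14% of 5.76 (9.6 − 3.84); the sample size section supports both figures. If dropout instead depends on a later Year 1 value with correlation 0.6 to 0.8 to Week 72 and log-odds of 0.5 to 1.0 per SD, the bias is 0.4 to 1.0. If dropout is unrelated to progression, it is zero.

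**3. Bias against the standard error.** SE = SD × √(1/n_early + 1/n_delayed). The re-randomisation ratio is not given; 1:2:2 is assumed, applied to 86.

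- 250 mg, 46 versus 17: 13.7 × √(1/46 + 1/17) = 3.89. Ratio 0.27/3.89 = 0.07 to 0.80/3.89 = 0.21.
- 1250 or 3500 mg, 86 versus 34: SE 2.78. Ratio 0.10 to 0.29.
- With 1:1:1 (29 per group), the SEs are 3.25 and 2.94, and the ratios are at most 0.25 and 0.27.

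A nominal 5% test would reject in 5.1% to 5.5% of null trials for 250 mg and 5.1% to 6.0% for the higher doses (1:2:2).

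**4. Precision lost up to Week 52.** With equal variances the scale cancels. At Week 52, for 250 mg under 1:2:2 (91/5 = 18.2), the SE ratio of same-dose to full placebo is √[(1/48 + 1/18.2)/(1/48 + 1/91)] = 1.54. For 1250 or 3500 mg (36.4) it is 1.32. Under 1:1:1 (30.3) the ratios are 1.30 and 1.41. The SE is therefore 30% to 54% larger.

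**5. Effect of coding placebo as one group through Week 52.** Approximate variance at Week 72: SD² × [1/n_early + (1 − ρ²)/n_delayed + ρ²/86], where ρ is the assumed correlation between Weeks 52 and 72.

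- 46 versus 17, ρ = 0.7: 13.7 × √(0.0217 + 0.0300 + 0.0057) = 3.28.
- ρ = 0.8: 3.07.

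Over both splits and ρ of 0.6 to 0.8, the SE falls by about 8% to 21%.

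**The case against.** Several points on the other side stand. For MDS-UPDRS the same-dose contrasts are optional and carry no alpha or power claim. The imaging population excludes anyone without a post-baseline scan, so the early-start imaging groups are not everyone randomised to that dose. Section 4.4 covers the same imaging analyses and defines only the pooled comparator, so the plan gives two accounts of imaging. The second limb of the early-start definition in 4.1 could be read as limiting early start to subjects who entered the extension. Grouping by assignment favours the other reading. If the restriction were meant, both sides would be selected after randomisation: the bias computed above would not apply as stated, but the contrast would still not be fully randomised.

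The bias is also small against the standard error. It compares raw means, and the covariates of the Year 1 model would absorb whatever selection baseline explains.

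Same-dose contrasts have a legitimate purpose, too: after Week 52 the pooled group mixes three doses, so only a same-dose contrast isolates the timing of the start. That argues for keeping them as supportive, not for using them at Weeks 24 and 52.

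A reader might infer that the Week 72 primary result or the overall type I error is compromised. The documents do not support that, because 4.3.2 makes the pooled group, with all placebo subjects, the primary comparator.

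**Conclusion.** The point holds for the same-dose contrasts, and it matters most for imaging, where 4.6.1 gives them first place with p-values at Weeks 24 and 52 and no caveat. They are not fully randomised comparisons on either reading of the early-start definition.

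The size is modest: about 0.3 to 0.8 MDS-UPDRS points at Week 72, or roughly 0.1 to 0.2 SE for 250 mg and up to about 0.3 SE for 1250 and 3500 mg. This rests on the SAP's dropout rate and SD and on assumed correlations, dropout odds and re-randomisation ratio. A reader might also infer a known bias for or against the drug. The direction depends on who leaves, which the documents do not say, and no imaging bias can be computed from them. The loss of precision up to Week 52 needs only the group sizes, equal variances and an assumed split.

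**What to change.** 1. Reconcile 4.4 with 4.6.1 so that the pooled delayed-start group, including placebo subjects who did not enter the extension, is the main imaging comparator, as it is for MDS-UPDRS.
2. Do not report same-dose contrasts at visits up to and including Week 52, in 4.3.1, 4.3.2, 4.6.1 or 4.6.2. Only the full placebo arm applies there.
3. Where same-dose contrasts are reported after Week 52, estimate them from one MMRM in which all placebo subjects form a single group through Week 52 and are split by Year 2 dose only afterwards. Label them supportive. Year 1 placebo dropouts with data then inform the common placebo means, and under the missing-at-random assumption already in the plan the selection is removed. The unstructured covariance set in the Year 1 SAP for imaging (5.5.5) and for MDS-UPDRS data after PD medication (5.3.2.3) suits this coding.
4. State in 4.1 whether early start includes subjects who did not enter the extension.

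The cost is SAP wording and a different coding of the treatment-by-time term, with no new data. The downside is a less standard model coding.
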